2.2 Secondary Objectives

1. To determine MR imaging correlates of peritumoral BBB disruption after MLA.
2. To identify serum biomarkers of peritumoral BBB disruption after MLA, which can be used to establish peritumoral permeability scores.
3. To determine the predictive value of the peritumoral permeability score for patient outcome as measured by 6PFS rate.

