14.0 STATISTICAL CONSIDERATIONS

Since we do not have any preliminary data for MR imaging, serum biomarkers, etc, it is not feasible to estimate sample size or provide power estimates. Therefore, this study is considered as a pilot study and the data collected will be used to design future studies. We propose six patients each arm as this is considered to be reasonable to recruit within the available a time frame.

In each arm, we will consider the following statistical analysis:

For the primary endpoint, MR imaging will be collected at the time points: pre-MLA (OPTIONAL), post-MLA, two-four weeks after MLA and every twelve weeks in Arm A; pre-MLA, post-MLA, two-four weeks after MLA and every eight weeks in Arm B. The linear regression model will used to investigate the correlation between MR imaging and peritumoral BBB disruption. To account for correlation among the repeated measures from the same patient, the longitudinal data will be analyzed with the use of linear generalized estimating equation (GEE). Whether the average measurements differ at the multiple time points will be evaluated through GEE model. Least-square means at each time points will be presented and standard errors will be calculated within the use of the GEE sandwich method when accounting for within-patient correlation.

Since we do not know which biomarkers will have better correlation with the Ktrans data from DCE and DSC-MRI and patients' survival outcome, we plan to determine the levels of all 3 biomarkers in a blinded fashion. Once both the Ktrans and biomarker levels are available, we will determine which biomarkers have the closest correlation that is statistically significant with the Ktrans. Pearson correlation coefficient (r) will be determined for each biomarker and Ktrans value. Biomarkers with higher correlation coefficient (r approaching 1) will be given higher priority. A minimum $r=0.5$ is required for inclusion for further analysis and will be used as a peritumoral

permeability score. This score will then be correlated with the patient outcome data (as measured by 6PFS rate) to determine whether it has a predictive value.

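### The biomarker selection rule uses plain Pearson r on repeated data without stating the unit of analysis; one of its two cut-offs is redundant, and pooling would often miss a marker that tracks Ktrans within patients

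*Combined protocol and SAP*

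**What the plan says.** Section 14.0 sets two conditions for a biomarker to enter the peritumoral permeability score. The first is significance: "we will determine which biomarkers have the closest correlation that is statistically significant with the Ktrans". The second is size: "A minimum $r=0.5$ is required for inclusion for further analysis". The statistic is plain Pearson: "Pearson correlation coefficient (r) will be determined for each biomarker and Ktrans value". Three biomarkers are screened (S100B, GFAP and BSE). The analyses are introduced with "In each arm, we will consider the following statistical analysis", and the sample size is given as "We propose six patients each arm".

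The section gives no alpha, no sidedness and no multiplicity rule for this step. It also does not say whether each patient contributes one pair or many. Repeat pairs exist by design: Sections 9.1 and 9.2 schedule serial MRI after MLA, with blood drawn on the day of the scan at the follow-up visits.

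The preceding paragraph of Section 14.0 does deal with clustering for the MR imaging data: "To account for correlation among the repeated measures from the same patient, the longitudinal data will be analyzed with the use of linear generalized estimating" equations. The biomarker step has no such provision.

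The rule serves secondary objective 2 in Section 2.2, "To identify serum biomarkers of peritumoral BBB disruption after MLA, which can be used to establish peritumoral permeability scores". The resulting score is then related to 6PFS under secondary objective 3.

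**The concern.** The rule can be read in two ways, and the two conditions interact differently in each. With one value per patient, six points per arm make the significance condition far stricter than 0.5. With all repeat samples pooled, the significance condition becomes easy to meet, and its p-value treats several samples from one child as independent.

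Pooling also blurs the question. Section 1.7 relies on the course of serum levels over time to show how long and how far the barrier is open. That is a within-patient question: does the serum level rise and fall with Ktrans in the same child? A pooled Pearson r mixes this with stable differences between children. Where those differences are large and unrelated to Ktrans, they dilute a real within-patient relation.

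At stake is which of the three markers is carried into the score, into the comparison with 6PFS, and into the future studies that this pilot is meant to inform.

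**Working it through.** **Inputs from the documents.** Six patients per arm, analysis by arm, three biomarkers, and the floor r = 0.5 (Section 14.0). From Section 9.1, if a patient does not progress, I count about 6 post-MLA scans in Arm A and about 15 in Arm B. The floor has no derivation in the plan, so there is no stated calculation to reproduce.

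**Assumptions.** Two-sided alpha of 5%. Five pairs per patient, which allows for some early progression. The intraclass correlation (ICC), meaning the share of variance that lies between patients, is set equal in biomarker and Ktrans at 0.3, 0.5 or 0.7. The documents give none of these.

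**Reading 1: one pair per patient, n = 6.**

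- Critical r = t / sqrt(n − 2 + t²). With 4 degrees of freedom t = 2.776, so r = 2.776 / sqrt(4 + 7.71) = 0.811.
- At one-sided 5% or two-sided 10% the critical value is 0.729.
- For r = 0.5, t = 0.5 × sqrt(4 / 0.75) = 1.155, giving two-sided p = 0.31. The Fisher-z 95% interval is −0.52 to 0.93.
- A marker that meets the significance condition has therefore already passed 0.5, and the floor has no effect.
- An unrelated marker passes in the positive direction 2.5% of the time; at least one of three independent markers passes 1 − 0.975³ = 7%.
- A marker with a true correlation of 0.7 passes in only 37% of trials.

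**Reading 2: pooled pairs, 6 × 5 = 30.**

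- Critical r at n = 30 is 0.361. The 0.5 floor is already above the critical value from 16 pairs (0.497), so the floor does the selecting and the significance condition adds nothing.
- I simulated 40,000 trials per setting. In the first two rows biomarker and Ktrans are unrelated. In the last two, the within-patient correlation is 0.8 and the patient baselines are unrelated.

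| | ICC 0.3 | ICC 0.5 | ICC 0.7 |
|---|---|---|---|
| No association: nominal 5% Pearson test rejects | 9% | 16% | 27% |
| No association: passes both conditions | 0.6% | 2% | 5% |
| Within-patient 0.8: expected pooled r, about 0.8 × (1 − ICC) | 0.56 | 0.40 | 0.24 |
| Within-patient 0.8: pooled r below 0.5, marker dropped | 27% | 54% | 71% |

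The third row explains the fourth. Only the within-patient share of the variance, 1 − ICC, carries the association, so pooling shrinks 0.8 towards zero.

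More samples do not cure this. At 15 pairs per patient the dropped share is 23%, 54% and 72%, and the nominal 5% test rejects 17%, 33% and 50% of the time.

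**Same data, within-patient correlation.** Each patient's own mean is subtracted from both variables before correlating. With five pairs per patient the median estimate is about 0.8 at every ICC, it falls below 0.5 in less than 1% of trials, and a 5% test of no association rejects 5% of the time.

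**The case against.** The best defence is that this is a pilot. Section 14.0 disclaims any power calculation and says that the data will be used to design later studies. Marker triage for a secondary objective drives no treatment decision, sample size or primary endpoint. Low sensitivity with six patients follows from the disclosed size, and under the one-pair reading no choice of coefficient cures it. All of this stands, and it limits the weight of the point.

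A reader might go further and infer that the rule lets false markers through. Each condition taken alone suggests so. At n = 6 an unrelated marker reaches r of at least 0.5 in 16% of trials, and at least one of three independent markers does so in 40%. Under pooling, the naive test rejects up to 27% of the time in the settings above. But the plan requires both conditions, and negative correlations cannot meet the floor. The joint pass rate for an unrelated marker is 2.5% at n = 6 and about 0.6% to 5% with 6 × 5 pairs. It goes above 10% only at an ICC of 0.9. False admission is not the main problem.

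Nor do the documents support saying that the rule cannot work, or that r = 0.5 can never qualify. A marker with r of 0.811 or more qualifies at n = 6. Alpha is unstated, so the 0.811 rests on a conventional level. If the arms were combined (n = 12), 0.5 would fail two-sided (p = 0.098) but just pass one-sided (p = 0.049), although the text specifies analysis by arm.

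The defence does not remove two facts: the unit of analysis is undefined, and the clustering recognised one paragraph earlier is ignored here.

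**Conclusion.** The point holds as a limited but real flaw in one secondary analysis. The unit of analysis for the biomarker–Ktrans correlation is not stated, and one of the two cut-offs is redundant under either reading by arm: the floor with one pair per patient, the significance condition once about 16 or more pairs are pooled.

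Under pooling the p-value is too small, at about 9%, 16% and 27% against a nominal 5%. The larger cost is that a marker following Ktrans closely within patients (correlation 0.8) is dropped in about 27%, 54% and 71% of trials. These figures rest on the assumed ICC of 0.3, 0.5 and 0.7, five pairs per patient, two-sided 5% and unrelated patient baselines. If patients hardly differed in their baselines, pooling would do little harm. A common time course after MLA in both variables was not simulated.

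A reader might infer that secondary objectives 2 and 3 cannot be answered at all. The documents do not support that. They promise preliminary data only, and objective 3 is limited by six 6PFS outcomes per arm whichever marker is chosen. What is affected is which markers are carried forward and how the p-values are read. No primary endpoint is touched.

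**What to change.** In Section 14.0, for the biomarker–Ktrans step only:

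- Replace plain Pearson with a within-patient measure on the pairs already collected. Either a repeated-measures correlation or a regression of log biomarker on Ktrans with patient-specific intercepts will do. State that the pairs are matched blood and MRI visits and that the patient is the independent unit.
- Do not regress biomarker change from baseline on the Ktrans level. The pre-MLA blood sample is scheduled but the pre-MLA scan is optional, so Ktrans may have no matching baseline.
- Report all three biomarkers with confidence intervals that respect clustering by patient. Sandwich standard errors are themselves unreliable with six patients, so a small-sample method is preferable.
- Rank the markers by the within-patient estimate instead of applying a significance gate.
- Label any relation between the score and 6PFS as descriptive.

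The cost is SAP wording and slightly more analysis, with no added patients, visits or samples. The downside is that the pilot ends with a ranking and wide intervals, not a pass/fail score.

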1.0 BACKGROUND AND RATIONALE

1.1 Pediatric Brain Tumors

Pediatric brain tumors comprise a heterogeneous group of tumors, including gliomas (high and low grade), medulloblastoma, ependymoma, primitive neuroectodermal tumor (PNET), atypical teratoid/rhabdoid tumor (ATRT), choroid plexus carcinoma, as well as other rarer tumors. Gliomas are the most common tumors in pediatrics, especially grade I (pilocytic astrocytoma) and grade II. High grade gliomas include anaplastic astrocytoma, glioblastoma (GBM), and mixed oligoastrocytomas. As with adults, high grade gliomas in pediatrics confer a poor prognosis. The current standard chemoradiotherapy for newly diagnosed high grade glioma produces only a modest survival benefit in pediatric patients, with less than 20% alive at five years [1]. All recurrent pediatric malignant tumors have a very poor prognosis with no standard and few effective therapeutic options available. Most children with relapsed disease will succumb within 3 years of recurrence with any malignant tumors. One of the challenges in treating brain tumors is the limitation of many agents to penetrate the blood brain barrier (BBB). Several methods to overcome BBB disruption have been attempted and currently undergoing studies, including intra-arterial chemotherapy administration, direct intratumoral/intracavitary placement of chemotherapy agents, and convection-enhanced delivery of agents, although a method with clear survival benefit has yet to be demonstrated [2].

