1.3.1 Prior Clinical Experience with MLA

We have had one of the largest clinical experiences using MLA in the country. To date we have done more than 80 cases, of which approximately two-thirds are high-grade glial neoplasms. In regards to adverse events, patients have experienced transient aphasia, transient hemiparesis, transient hyponatremia, and a documented case of lower extremity deep venous thrombosis. Patients with aphasia or hemiparesis improved over time with steroid therapy. Hyponatremia resolved spontaneously. One patient experienced fatal meningitis. Subsequent in-depth analysis revealed that this patient's meningitis was due to an operating room infrastructure-related contamination and not due to equipment contamination related to performance of the MLA procedure.

1.4 MLA followed by Standard of Care in Newly Diagnosed Glioma Patients (Arm A)

MLA offers an alternative to some patients with tumors that are unresectable. Complete surgical resection of grade I and II gliomas have a >90% overall survival, although complete resection is not always possible due to the location of the tumor. For tumors with less than a complete resection, chemotherapy or radiation therapy is offered for progressive

and/or symptomatic tumors. For high grade gliomas, patients who have a complete resection of the enhancing tumor at time of diagnosis [29, 30] or at relapse have a longer survival compared to those with residual disease [31]. In this arm of the study, patients with any grade glioma who are candidates for MLA will undergo this procedure followed by standard of care treatment.

1.5 MLA followed by Doxorubicin and Etoposide in Relapsed Malignant Tumor Patients (Arm B)

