2.0 OBJECTIVES

2.1 Primary Objectives

1. To determine progression-free survival (PFS) and overall survival (OS) of patients with new diagnosis glioma who are candidates for MLA (Arm A).
2. To determine 6-month progression-free survival (6PFS) in patients who receive doxorubicin immediately following MLA and low-dose etoposide as maintenance therapy in patients who are candidates for MLA with any type relapsed malignant brain tumors (Arm B).
3. To evaluate quality of life (QOL) using Karnofsky or Lansky performance status in patients following MLA and in patients who receive doxorubicin and maintenance etoposide after MLA.

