3.0 PATIENT SELECTION

3.1 Inclusion Criteria – Arm A

1. Presumed pediatric gliomas (grades I-IV) on MRI that are determined to be candidates for MLA by the treating neurosurgeon.
2. Age 3 to \leq 21
3. Karnofsky/Lansky performance status \geq 60%, see Appendix 1.

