5.0 TREATMENT PLAN

5.1 Study Summary

5.1.1 Arm A

Six patients enrolled to this study will be in Arm A; patients may be enrolled to Arm A at any time throughout the lifetime of the study. Arm A patients will undergo MLA and will be followed with standard of care therapy at the discretion of the treating physician.

Arm A patients will undergo DSC and DCE-MRI at the following time points along with standard of care imaging:

- no more than 3 weeks prior to MLA (OPTIONAL)
- within approximately 4 days after MLA
- 2-4 weeks after MLA
- Every 12 weeks (+/- 7 days) for the first year or until disease progression (see Section 9.1)

Arm A patients will have 7 ml of blood drawn at the following time points:

- Before MLA; this sample can be collected any time during the 3 days before or the day of the procedure until the start of the procedure
- Within approximately 3 days after MLA
- 2-4 weeks (+/- 3 days) after MLA (at time of DSC/DCE-MRI)
- Every 12 weeks (+/- 7 days) at time points correlating with MRIs for the first year or until disease progression

The purpose of these blood draws is to measure serum levels of brain-specific factors (S100B, GFAP, and BSE) and cytokine levels. PBMC (for the pre- and post-MLA samples) will also be isolated to determine the phenotypes and functions of peripheral blood immune cells following MLA (see Section 9.2-9.4).

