9.5 OPTIONAL Biopsy for Tumor-Specific Functional Activity of Peripheral Blood Immune Cells

The patients in both arms may have a biopsy immediately before MLA. Specimens not used for histologic diagnosis will be cryopreserved in the tumor bank for later processing. Should our studies by either flow cytometry or qRT-PCR described in Section 9.4 show evidence of lymphocyte activation, then after PBMC samples have been obtained, we will test T cell reactivity in an in vitro stimulation assay. Dendritic cells matured from monocytes as described in Section 9.3 above will be incubated with freeze-thawed biopsy specimen lysate for 2 days and subsequently incubated with T cells purified from PBMC

using CD3/CD8-positive microbeads. Five days after stimulation, T cell reactivity will be assessed by ELISPOT assay for IFN- γ stimulation. This study will test whether MLA stimulates increased tumor-specific T cell recognition and activation. As in Section 9.4, the amount of blood drawn from some patients may be limited and could limit or ability to conduct these functional assays.

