PFS and OS will be estimated by Kaplan-Meier product limit method. The progression-free survival and overall survival probabilities at certain time points (e.g. 3 months, 6 months) will be presented as well. The difference in OS between Arm A and the historical control of bevacizumab alone will be compared by log-rank test. The quality of life (QOL) using Karnofsky or Lansky performance status will be characterized by summary statistics (mean, standard deviation and range).

The tumor-specific immune responses are collected at pre and post-MLA treatment. Paired t-test will be used to determine the effects of MLA treatment on patient's tumor-specific immune responses. Cox proportional hazard model will be used to determine the relationship between the duration of MLA-induced BBB disruption and PFS.

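### The log-rank test of Arm A overall survival against an undefined bevacizumab historical control cannot show an MLA effect in either direction

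*Combined protocol and SAP*

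**What the plan says.** The statistical section commits to one between-group survival comparison: "The difference in OS between Arm A and the historical control of bevacizumab alone will be compared by log-rank test" (section 14.0). It states no alpha, sidedness, stratification by grade or method for handling historical data.

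The other places that bear on it are:

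- **Objective (2.1).** The first primary objective is "To determine progression-free survival (PFS) and overall survival (OS) of patients with new diagnosis glioma who are candidates for MLA (Arm A"). It asks for estimation and names no comparator.
- **Population (3.1).** "Presumed pediatric gliomas (grades I-IV) on MRI that are determined to be candidates for MLA by the treating neurosurgeon". Ages run from 3 to 21, and section 5.1.1 sets the arm at six patients.
- **Treatment (5.1.1).** "Arm A patients will undergo MLA and will be followed with standard of care therapy at the discretion of the treating physician".
- **Confirmation of grade (9.5).** Biopsy is optional: "The patients in both arms may have a biopsy immediately before MLA".
- **Prognosis (1.1 and 1.4).** For newly diagnosed high-grade glioma the protocol cites a poor outlook, "with less than 20% alive at five years". For low grade it says "Complete surgical resection of grade I and II gliomas have a >90% overall survival", without a time point.

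Bevacizumab appears in only one other place in the text available for review, the Arm B exclusion for recent prior use (3.4). Arm B itself receives doxorubicin and then etoposide (5.4). None of the 60 reference titles names bevacizumab.

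**The concern.** A historical comparison can support a statement about MLA only if the control resembles Arm A in everything except MLA. Here nothing ties the two groups together. The control is defined by a drug that Arm A is not assigned. Its disease setting, newly diagnosed or recurrent, is unstated. Arm A spans grades whose survival differs several-fold on the protocol's own figures. With six patients, one or two more low-grade cases can change the result.

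The sentence also cannot be run as it stands. A two-sample log-rank test needs survival times for the control patients. A one-sample version needs a reference survival curve. The plan identifies neither, so someone would have to choose a control later, possibly after seeing the Arm A data.

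No sample size, stopping rule or treatment decision depends on this test. What is at stake is a misleading p-value on a primary objective, in a pilot that section 14.0 says will inform the design of later studies.

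**Working it through.** The documents give no effect size, event count or control survival for this test, so there is no planned figure to reproduce. The check asks how often the test would be significant **if MLA had no effect at all**.

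**Inputs from the documents**
- Arm A: n = 6 (5.1.1). Follow-up: up to 5 years after registration (5.9).
- High-grade 5-year OS: taken as 20%, the upper bound in 1.1. Sensitivity value 10%.

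**Assumptions**
- Low-grade 5-year OS of 90% or 80%. Section 1.4 gives above 90% for completely resected tumours with no time point, while Arm A is aimed at a different group: "MLA offers an alternative to some patients with tumors that are unresectable".
- Control n = 50, with 3-year OS of 10%, 25%, 40% or 50%.
- Exponential survival, censoring at 5 years, two-sample log-rank test, |z| > 1.96.

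**Yearly hazards**
- High grade: −ln(0.20)/5 = 0.322. At 10%: −ln(0.10)/5 = 0.461.
- Low grade: −ln(0.90)/5 = 0.021. At 80%: −ln(0.80)/5 = 0.045.
- Control: −ln(S3)/3 = 0.768, 0.462, 0.305 and 0.231 for S3 = 10%, 25%, 40% and 50%.

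**Expected Arm A deaths by 5 years** (low grade 90%)
- No low-grade patients: 6 × 0.8 = 4.8
- Three: 3 × 0.8 + 3 × 0.1 = 2.7
- Six: 6 × 0.1 = 0.6

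Grade mix alone thus moves the expected deaths eightfold.

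**Chance that Arm A is declared significantly better** (nominal 2.5%; 20,000 runs per cell, Monte Carlo standard error at most √(0.25/20,000) = 0.35 points). Low-grade OS is 90%, with 80% in brackets.

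| Control 3-year OS | 0 low grade | 3 low grade | 6 low grade |
|---|---|---|---|
| 10% | 43% (43%) | 96% (92%) | 100% (100%) |
| 25% | 9% (9%) | 64% (54%) | 99% (96%) |
| 40% | 1% (1%) | 21% (16%) | 93% (78%) |
| 50% | 0% (0%) | 7% (5%) | 77% (54%) |

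Changing the control size to 25 or 100 moves these cells by at most about 7 points.

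**Chance that Arm A is declared significantly worse**
- No low-grade patients, control 3-year OS 25%, 40%, 50%: 1%, 6%, 15%.
- The same with high-grade 5-year OS of 10%: 5%, 21%, 38%.
- A control with 90% 5-year OS, and 0, 3 or 6 low-grade patients: 99%, 73%, 5% (4,000 runs per cell).

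**Perfectly matched control.** With no low-grade patients and the control given the same hazard (3-year OS 0.2^0.6 = 38%), the test still gives 1.3% for and 5.4% against Arm A. The normal approximation is poor with six patients.

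**A non-significant result is no more informative.** Suppose all six Arm A patients and all controls die. Schoenfeld power for a hazard ratio of 0.50 with 30 controls is Φ(√(36 × 1/6 × 5/6) × ln 2 − 1.96) = Φ(1.55 − 1.96) = 34%. With 1,000 controls it is 40%. Against a fixed reference curve with six events, 80% power needs a hazard ratio of exp(−(1.96 + 0.84)/√6) = 0.32.

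**The case against.** The best opposing case has five parts.

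1. *A log-rank test need not use control patient data.* This is correct for the one-sample version, and the plan does not say which version is meant. The gap is that neither a dataset nor a reference curve is named. The simulated percentages describe the two-sample version only. Switching versions does not remove the mismatch of drug, grade and setting.

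2. *OS is not labelled the primary endpoint.* Section 14.0 attaches that term to MR imaging. OS is a primary objective in section 2.1, and that is the term used here.

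3. *The percentages are illustrations.* This stands. Control size, control survival, low-grade survival and the number of low-grade patients are all assumed. In the table's range of controls, results against Arm A arise almost only when no patient is low grade. With three low-grade patients they are well under 1%, unless the control survives much better, as in the 90% example. The figures show how far the result depends on unstated inputs. They do not predict what will happen.

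4. *This is a six-patient pilot with no power claim.* That limits the harm to interpretation. It does not make the test interpretable.

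5. *Physician-choice care could include bevacizumab, and a control definition might sit in text not available here.* Use of bevacizumab after MLA is not barred, but it would blur the contrast further. The front matter and, judging from the contents list, section 1.8 on immune activation were not in the text reviewed. A definition there is unlikely, and it would not make a bevacizumab-alone series comparable with a mixed-grade, newly diagnosed arm.

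**Conclusion.** The concern holds and should be fixed before analysis. The planned comparator is undefined and is built on a drug that neither arm is assigned, so neither a significant nor a non-significant p-value can be attributed to MLA. With no MLA effect, the chance of a significant result favouring Arm A runs from about 0% to 100% across the assumed controls and grade mixes. The chance of one against it reaches 15% with no low-grade patients in the table's range of controls, and 38% if high-grade 5-year OS is 10%. These sizes rest on exponential survival, five years of follow-up and assumed control and low-grade survival. The conclusion that the p-value is uninterpretable does not depend on those values.

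**What to change.** Delete the bevacizumab log-rank sentence from section 14.0 and replace it with text such as:

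> Arm A OS and PFS will be estimated by Kaplan-Meier with 95% confidence intervals. A patient-level listing will give tumour grade (histological where a biopsy exists, otherwise presumed from MRI), treatment after MLA, survival time and status. Any summary by grade group is descriptive. No formal comparison with a historical control will be made.

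State the OS time origin at the same time, since section 12.3.6 defines only PFS. If historical context is wanted, cite a sourced, newly diagnosed series matched on grade and age, descriptively and without a test. A sponsor who insists on a test would need to name such a series in advance, with its time origin and method, and label the result exploratory. With six patients it would still have little power.

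The cost is one replaced sentence and one listing with a column for how grade was determined. The sponsor gives up a p-value that could not have been interpreted, and the estimation objective in section 2.1 is still met.
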